4.2 Secondary Efficacy Endpoints

Duration of Response (DoR)

Duration of response is defined as the time from the start date of first observed CR or PR (subsequently confirmed) to the date of first documented radiographical progression of disease using RECIST v1.1 or death from any cause, whichever comes first. DoR will be calculated for subjects who are responders, i.e., those who achieve a confirmed CR or PR.

DoR in days will be calculated as:

DoR (days) = [Date of PD, or Death, (whichever is earlier)] – (First Date of PR/CR) + 1 DoR in months will be calculated as:

DoR (months) =
$$[12 \times DoR (days)]/365.25$$

Responders who have not experienced disease progression or death at the time of the analysis will be censored at the date of the last tumor assessment. If no tumor assessments are available after the date of the first occurrence of response, the subject will be censored on the date of the first occurrence of the response.

Progression-Free Survival (PFS)

Progression-free survival is defined as the time from the date of first dose (study day 1) of study treatment to the first documented radiographical progression of disease using RECIST v1.1, or death from any cause, whichever comes first.

PFS in days will be calculated as:

PFS (days) = [Date of PD or Death (whichever is earlier)] – (First Dose Date) + 1

PFS in months will be calculated as:

PFS (months) =
$$[12 \times PFS (days)]/365.25$$

The following table summarizes the PFS censoring rules:

Table 3: Progression-Free Survival Censoring Rules

	Primary Analysis (Censoring Rules)	Sensitivity Analysis (Censoring Rules)
No PD, No death	Censored at last tumor assessment. If no evaluable tumor assessment, censored on the first dose date.	Censored at last tumor assessment. If no evaluable tumor assessment, censored on the first dose date.
PD or death after 1 missed tumor assessment	PFS event at the date of PD or death	PFS event at the date of PD or death
PD or death after 2 or more missed tumor assessments	Censored at last tumor assessment prior to PD or death	PFS event at the date of PD or death
PD or death after NACT	Censored at the last tumor assessment prior to NACT	PFS event at the date of PD or death
No PD, no death, NACT initiated	Censored at the last tumor assessment prior to NACT	Censored at last tumor assessment regardless of NACT

Overall Survival (OS)

Overall survival is defined as the time from the date of first dose (Dose 1) of study treatment to the date of death from any cause.

OS in days will be calculated as:

$$OS (days) = Date of Death - First Dose Date + 1$$

OS in months will be calculated as:

OS (months) =
$$[12 \times OS (days)]/365.25$$

Subjects who are alive at the time of analysis or lost to follow-up will be censored on the date the subject is last known to be alive based on data collected in the database. The maximum follow-up is 15 months from the first dose of study treatment for each subject.

4.3 Safety Endpoints

Treatment-Emergent Adverse Events (TEAEs)

Adverse events (AE) will be coded using the Medical Dictionary for Regulatory Activities (MedDRA) dictionary v24.1 or later. Severity will be graded according to the National Cancer Institute (NCI) Common Terminology Criteria for Adverse Events (CTCAE) v5.0. All AEs, complaints, or symptoms that occur from the time of written informed consent

through the 90-day safety follow-up are to be recorded on the appropriate case report form (CRF).

A TEAE is any adverse event with an onset date on or after the date of first dose of study treatment through 90-day safety follow-up or the initiation of new anti-cancer therapy, whichever is earlier. TEAEs will be summarized in the safety analysis.

Dose-Limiting Toxicities (DLTs)

A dose-limiting toxicity (DLT) is defined as the occurrence of any of the events listed in Section 4.1.5 of the protocol that are assessed by the investigator to be possibly, probably, or definitely related to study treatment. The DLT window of observation for the purposes of dose escalation will be Cycle 1 defined as a subject receiving 3 doses of E-602 for monotherapy cohorts and 3 doses of E-602 and 1 dose of cemiplimab for combination therapy cohorts.

Exposure to Treatment

Exposure to E-602 and cemiplimab will be summarized separately. The following variables will be derived for each drug.

Total Treatment Duration will be calculated as:

Total Treatment Duration (days) = Date of Last Dose – Date of First Dose + 1

Total Treatment Duration (months) = $12 \times \text{Total Treatment Duration (days)}/365.25$

Actual Dose Administered (mg) will be calculated as:

Actual Dose Administered (mg) = Actual Cumulative Dose Administered up to the Date of Last Dose

Relative Dose Intensity (RDI) is the percentage of actual dose administered relative to the cumulative dose planned through to treatment discontinuation.

RDI will be calculated as follows:

$$RDI = 100\% x (d/D)$$

where d (mg) is actual total dose administered and D (mg) is cumulative dose planned. D is the cumulative dose that would be administered if there were no modification to dose or schedule.

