8.3.1. Time Period and Frequency for Collecting AE and SAE Information

All AEs and SAEs will be collected from the signing the informed consent form (ICF) until the final safety follow-up visit at the timepoints specified in the SoA (Section 1.3). If prior to completing the 90-day safety follow-up period a subject begins a new cancer treatment, no further safety follow-up is required.

All SAEs will be recorded and reported to the Sponsor or designee immediately and under no circumstance should this exceed 24 hours, as indicated in Appendix 10.3. The investigator will submit any updated SAE data to the Sponsor or designee within 24 hours of it being available.

Investigators are not obligated to actively seek information on AEs or SAEs after conclusion of the study participation. However, if the investigator learns of any SAE, including a death, at any time after a subject has been discharged from the study, and he/she considers the event to be reasonably related to the study treatment or study participation, the investigator must promptly notify the Sponsor or designee.

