9.2.4.2. Treatment Emergent Adverse Events

All adverse events will be coded to a system organ class and a preferred term based on the Medical Dictionary for Regulatory Activities (MedDRA) version 24.0 or later.

Treatment-emergent adverse events (TEAEs) are defined as AEs with an onset date on or after the date of first dose of study treatment until 90 days after the last dose.

Subject incidence of all treatment-emergent adverse events, serious adverse events, adverse events leading to discontinuation of treatment, and fatal adverse events will be tabulated by system organ class and preferred term.

The number and percent of subjects reporting TEAEs will be evaluated overall and by dose level and will also be tabulated by severity and relationship to study treatment. The severity of each adverse event will be graded using The Common Terminology Criteria for Adverse Events (CTCAE) version 5.0 or later criteria.

For the Phase 1 component of the study, DLTs (if any) will be summarized by dose and will be listed separately.

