8 CHANGES FROM PROTOCOL-SPECIFIED ANALYSIS

There are no changes from the analysis specified in protocol v8.0.

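### SAP 4.3 ends the treatment-emergent window at new anti-cancer therapy, protocol 9.2.4.2 does not, and SAP 8 declares no change; the effect is confined to events still recorded after the switch

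*SAP*

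**What the plan says.** **Definition in the protocol.** Section 9.2.4.2 defines TEAEs as "AEs with an onset date on or after the date of first dose of study treatment until 90 days after the last dose". Subsequent therapy plays no part.

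**Definition in the SAP.** Section 4.3 starts at the same point but closes the window "through 90-day safety follow-up or the initiation of new anti-cancer therapy, whichever is earlier". The sentence before it has AEs recorded on the CRF from consent through the 90-day follow-up, with no exception for NACT.

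**Collection rule.** Protocol 8.3.1 states: "If prior to completing the 90-day safety follow-up period a subject begins a new cancer treatment, no further safety follow-up is required". Protocol 4.1.1 ends monitoring for immune-related toxicity at the same point. For SAEs learned of after discharge, 8.3.1 keeps a duty: where "he/she considers the event to be reasonably related to the study treatment or study participation, the investigator must promptly notify the Sponsor" or its designee.

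**Outputs.** SAP 6.4.2 plans tables of TEAEs, treatment-related TEAEs and TEAEs by maximum severity, and a listing of fatal TEAEs. AEs on the CRF that are not TEAEs are listed only. Separate tables cover SAEs, SAEs by severity and treatment-related SAEs, with no window given.

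**Declared changes.** SAP 1 promises to document major modifications. SAP 8 says: "There are no changes from the analysis specified in protocol v8.0".

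**The concern.** The two documents classify the same recorded event differently, and the SAP does not say so. The SAP's cut ignores causality: an AE that the investigator attributes to E-602 or cemiplimab leaves the TEAE and treatment-related TEAE tables because the next therapy has started.

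AE incidence is a primary endpoint in Phase 1 and a secondary one in Phase 2. Protocol 4.1.3 names late immune-related toxicity as a reason for the 90-day follow-up, and 8.3.7 makes potential immune-related toxicities the events of special interest. Removing recorded related events can lower the reported TEAE incidence or leave it unchanged; it cannot raise it. A reader who trusts SAP 8 would take the tables to follow the protocol's definition.

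**Working it through.** There is no plan figure to reproduce. The check sets the definitions against the output list and asks what happens to each kind of event.

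**Step 1: classify by onset date.** Both definitions turn on onset, not on when the event is reported.

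| Event, within 90 days of last dose | Protocol 9.2.4.2 | SAP 4.3 | Where it appears under SAP 6.4.2 |
|---|---|---|---|
| Onset before NACT, reported after it | TEAE | TEAE | TEAE tables |
| Onset after NACT, non-serious, related, recorded | TEAE | not a TEAE | listing only |
| Onset after NACT, serious, related, recorded | TEAE | not a TEAE | out of TEAE tables; possibly in SAE tables |
| Onset after NACT, fatal, recorded | TEAE | not a TEAE | out of the fatal-TEAE listing; possibly in SAE outputs |
| Onset after NACT, never recorded | cannot be counted | cannot be counted | nowhere |

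For example, with NACT on day 30 after the last dose and a recorded related AE on day 40, the protocol counts the event as treatment-emergent (40 ≤ 90). The SAP does not (40 > 30).

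**Step 2: can such events be recorded at all?** Yes, though not systematically.
- Protocol 7.1 makes starting another cancer therapy a reason for discontinuation and then requires an end-of-treatment visit. The schedule of activities has AEs assessed there. That visit can fall after NACT, and the relief in 8.3.1 concerns safety follow-up.
- Related SAEs learned of after discharge must still be notified (8.3.1).
- Early discontinuers are contacted every 3 months (4.1.3), and cause of death is collected (8.3.6).

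**Step 3: the SAE tables.** SAP 4.3 says TEAEs are what the safety analysis will summarise, which could imply a TEAE restriction throughout. The SAE table titles in 6.4.2 carry no such restriction. The text supports either reading.

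**Step 4: size.** The number of affected events would need the share of subjects starting NACT within 90 days, the timing, and the rate at which later events are recorded. The documents give none of these, so no count follows.

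What can be stated is the effect of one affected subject on one incidence figure. SAP 6.4.2 counts each preferred term once per subject, so a post-NACT event changes overall incidence for that term only if the subject had no earlier TEAE of the same term. In that case the change is 1/n:
- escalation cohort of 6: 1/6 = 16.7 percentage points;
- cohort at the backfill ceiling of 15: 1/15 = 6.7 points;
- all 87 planned Phase 1 subjects: 1/87 = 1.1 points.

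These are sensitivities per subject, not estimates of how often this happens.

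**Step 5: a smaller gap.** The SAP ties the end of the window to a follow-up visit with a ±7-day allowance (days 83 to 97), whereas the protocol uses 90 days after the last dose.

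**The case against.** The strongest reply is that the SAP's cut follows the protocol's own observation rule. Required safety follow-up and immune-toxicity monitoring both end when another cancer therapy begins. After that, capture is uneven and attribution is confounded by the new agent, so closing the window there is a defensible analysis choice. It could also be argued that this is not a major modification in the sense of SAP 1.

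Much of this stands. It limits the effect to events recorded without systematic follow-up, and it makes the cut a legitimate option. It does not remove the conflict: the protocol contains both the relief from follow-up and an uncut TEAE definition. Nor does it make the statement in SAP 8 accurate.

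Four stronger readings are tempting, and the documents do not support them.
- *The days between NACT and day 90 measure what is lost.* They measure a shorter window. Follow-up in that period is not required under either definition, so the days do not translate into lost events, and an assumed share of subjects switching early has no anchor in the documents.
- *Late related SAEs vanish from the incidence tables.* They leave the TEAE tables but may remain in the SAE tables.
- *Anything reported at a visit after NACT is excluded.* Onset decides, so an event that began earlier stays a TEAE.
- *Dose escalation is affected.* DLTs are confined to Cycle 1 (protocol 4.1.5, SAP 4.3).

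**Conclusion.** The mismatch is real and SAP 8 is wrong as written. The SAP's window is narrower than the protocol's for any subject who starts NACT within 90 days of the last dose.

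The practical effect is limited to events that are recorded anyway, with onset after NACT and inside the 90 days. These are mainly non-serious related AEs, which drop to a listing, and fatal events, which drop out of the fatal-TEAE listing. Related SAEs may be unaffected, depending on a window that the SAP does not state.

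The number of events cannot be derived. The direction is known: TEAE incidence is either unchanged or too low relative to the protocol's definition. The conclusion assumes only that some post-NACT events reach the CRF, which the end-of-treatment visit and the SAE duty make foreseeable. It merits correction because the endpoint is primary in Phase 1 and the remedy is cheap; it does not undermine the safety analysis as a whole.

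**What to change.** Choose one of two routes.

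1. **Adopt the protocol window.** In SAP 4.3, count every recorded AE with onset from first dose to 90 days after the last dose as a TEAE, and flag those with onset after NACT. This also removes the dependence on the follow-up visit date.
2. **Keep the cut and declare it.** Retain the NACT limit for the main TEAE tables, enter it in SAP 8 as a departure from protocol 9.2.4.2 with the reason, and additionally tabulate treatment-related AEs, SAEs and fatal AEs to 90 days after the last dose regardless of NACT, with post-NACT events flagged.

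Under either route, state in SAP 6.4.2 the window for the SAE tables and whether they are restricted to treatment-emergent events.

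The cost is SAP wording, one flag in the AE dataset and, under route 2, a few extra tables. No new data are collected. The downside is that a few events with mixed attribution and non-systematic capture enter the tables; the flag lets a reader see them and set them aside.

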4.4 Other Definitions

Study Day 1

This is the day of the first dose of E-602 in monotherapy or first dose of either cemiplimab or E-602 in combination.

Baseline

Unless stated otherwise, the baseline value for any variable in the statistical analysis is defined as the last non-missing measurement prior to the first administration of study treatment.

Change from Baseline

Change from baseline is the arithmetic difference between any post-baseline assessments (i.e., assessments made after the first dose) and the baseline value.

Change from Baseline = Post-baseline Value – Baseline Value.

Visit Windows

Safety parameters such as laboratory values and vital signs are collected at certain scheduled visits over time. By-visit summaries are planned in the analysis. The definition of visit windows should cover the entire time to allow the potential for all scheduled and unscheduled visit data to be included in the by-visit analysis. For example, hematology and chemistry panels are scheduled on days 1, 8, and 15 in each cycle with a +/-2 days variation per protocol. The following visit windows may be defined for a particular Cycle X.

```
Cycle X Visit 1 = Days 1-4 in Cycle X

Cycle X Visit 2 = Days 5-12 in Cycle X

Cycle X Visit 3 = Days 13-21 in Cycle X.
```

If the start of the next cycle after Cycle X is advanced or delayed, Cycle X Visit 3 window is defined up to the day before the first day of the next cycle.

When two values are included in a visit window, the worst value (minimum or maximum depending on which direction is worse for the parameter of interest) will be used.

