- 9. Vital signs (pulse, body temperature, blood pressure, and oxygen saturation via pulse oximetry) should be obtained while breathing room air. Vital signs should be obtained at screening and on Cycle 1 Day 1 (predose and 1 (± 15 minutes), 2 (± 15 minutes), 4 (± 30 minutes), and 6 hours (± 30 minutes) after the start of E-602 infusion), Cycle 1 Day 8 (predose), Cycle 2 Day 1 (predose and 1 (± 15 minutes), 2 (± 15 minutes), 4 (± 30 minutes) and 6 hours (± 30 minutes) after the start of E-602 infusion), and predose at all other visits as noted.
- 10. Medical history includes cancer history including PD-L1 and tumor molecular mutation status, previous cancer therapies, review of systems, past and current medical conditions.
- 11. See Appendix 10.2 for the laboratory tests required. Cycle 1 Day 1 laboratory tests may be performed up to 72 hours prior to Day 1 to ensure results are available for review prior to dosing. Thyroid panel is required every other cycle, beginning with Cycle 1 (e.g., Cycle 1 Day 1, Cycle 3 Day 1, Cycle 5 Day 1, etc.).
- 12. Plasma samples for E-602 concentrations will be collected at time points described in Section 8.4. An unscheduled plasma PK sample should be collected in the event of an infusion related reaction.

- Protocol Number: PAL-E602-001 Version 8.0, 24 August 2023
- 13. Plasma samples for ADA analysis will be collected pre-dose. An unscheduled plasma ADA sample should be collected in the event of an infusion related reaction.
- 14. Either serum or urine pregnancy test is allowed. The choice of test is at the investigator's discretion.
- 15. Physical examination will include, at a minimum, the assessment of cardiovascular, respiratory, gastrointestinal, dermatological and neurological systems along with the lymph nodes and liver. Physical examination should be performed during screening, within 72 hours of or on Cycle 1 Day 1 and on Day 1 of each subsequent cycle.

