6.4.4 Vital Signs

Vital signs measurements (systolic and diastolic blood pressure, pulse rate, oxygen saturation, body temperature, and weight) will be summarized using descriptive statistics including absolute measurements and changes from baseline by visit.

All vital sign assessments will be presented in a by-subject listing.

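### The worst-value-in-window rule, applied to serial vital signs, builds a false mean change from baseline into visits with three to five readings (0.85 to 1.16 same-day SD)

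*SAP*

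**What the plan says.** SAP 4.4 (Visit Windows) covers both kinds of safety data: "Safety parameters such as laboratory values and vital signs are collected at certain scheduled visits over time". The windows are meant to "allow the potential for all scheduled and unscheduled visit data to be included in the by-visit analysis". The example given includes "Cycle X Visit 1 = Days 1-4 in Cycle X". The section then sets the tie rule: "When two values are included in a visit window, the worst value (minimum or maximum depending on which direction is worse" for the parameter) is to be used.

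The same section fixes baseline as one value, which "is defined as the last non-missing measurement prior to the first administration of study treatment". It also defines the change: "Change from baseline is the arithmetic difference between any post-baseline assessments (i.e., assessments made after the first dose) and the baseline value".

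SAP 6.4.4 says that vital signs "will be summarized using descriptive statistics including absolute measurements and changes from baseline by visit". Protocol 9.2.4.4 plans the same kind of summary. Neither mentions a time point within a visit.

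The protocol has two vital-sign schedules. Footnote 9 of section 1.3.1 (Phase 1 monotherapy) reads "Vital signs should be obtained at screening and on Cycle 1 Day 1 (predose and 1", and continues with 2, 4 and 6 hours; Cycle 2 Day 1 has the same five times. Footnote 9 of section 1.3.2 (Phase 1 combination and all of Phase 2) asks for predose, 1, 2 and 4 hours on Cycle 1 Day 1, and predose, 1 and 4 hours on Cycle 1 Day 8. Under both schedules every other dosing visit has one predose reading.

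**The concern.** The most extreme of several readings is being compared with a single baseline reading. Even if nothing has changed, the extreme of several readings lies away from the subject's mean while a single reading does not, so the mean change is off zero. The number of readings per window is set by the schedule and differs by visit, so the artefact comes and goes across visits.

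It appears on infusion days with post-dose monitoring, where a reader will look for a drug effect. Protocol 2.3 reports infusion-related reactions in 12 of 26 treated subjects, at doses of 10 mg/kg or more, so these tables will be read closely. A real post-infusion change could not be separated from the artefact.

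The SAP also does not say which direction is worse for blood pressure, pulse or temperature. Each can be abnormal either way, so even the sign of the shift is open.

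**Working it through.** The plan states no figure here, so there is nothing to reproduce.

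**Step 1. Post-baseline readings per window (k).** SAP 4.4 counts only assessments after the first dose as post-baseline. The Cycle 1 Day 1 predose reading therefore drops out of the change, while predose readings at later visits count.

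| Schedule | Visit | Readings taken | k |
|---|---|---|---|
| Phase 1 monotherapy | C1D1 | predose + 4 | 4 |
| Phase 1 monotherapy | C2D1 | predose + 4 | 5 |
| Phase 1 combination, Phase 2 | C1D1 | predose + 3 | 3 |
| Phase 1 combination, Phase 2 | C1D8 | predose + 2 | 3 |
| Both | other visits | 1 | 1 |

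**Step 2. Expected shift with no true change.** Assume normal readings, and let s be the same-day reading-to-reading SD. The mean of the worst of k readings minus one baseline reading is s × E_k, where E_k = ∫ x · k · φ(x) · Φ(x)^(k−1) dx. Numerical integration gives:

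- k = 1: 0
- k = 2: 0.564
- k = 3: 0.846
- k = 4: 1.029
- k = 5: 1.163

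A simulation of 1,000,000 subjects with independent readings gave 0.846, 1.031 and 1.163 for k = 3, 4 and 5.

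**Step 3. Same-day correlation.** Readings hours apart in one person share a day effect. If their correlation is ρ and S is the total within-subject SD, then s = S × √(1−ρ), and the shift is S × √(1−ρ) × E_k:

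| ρ (assumed) | k = 3 | k = 4 | k = 5 |
|---|---|---|---|
| 0 | 0.85 S | 1.03 S | 1.16 S |
| 0.25 | 0.73 S | 0.89 S | 1.01 S |
| 0.5 | 0.60 S | 0.73 S | 0.82 S |
| 0.75 | 0.42 S | 0.51 S | 0.58 S |

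**Step 4. Illustration in pulse units.** Assume a pulse SD of 6 to 10 bpm (not in the documents) and k = 4. If that is the same-day SD, the shift is 1.03 × 6 = 6.2 to 1.03 × 10 = 10.3 bpm. If it is the total within-subject SD, the shift is 4.4 to 7.3 bpm at ρ = 0.5 and 3.1 to 5.1 bpm at ρ = 0.75. It is upward if high is called worse and downward if low is.

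**Step 5. Pattern across visits and schedules.** In units of s, Phase 1 monotherapy shows 1.03 at C1D1, 0 at C1D8 and 1.16 at C2D1. Phase 1 combination and Phase 2 show 0.85, 0.85 and 0. Cohorts 104 and 111, both at 20 mg/kg E-602, would thus differ at all three visits with no difference in effect: by 1.03 − 0.85 = 0.18 at C1D1, 0.85 at C1D8 and 1.16 at C2D1.

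**Step 6. Laboratory values.** Scheduled panels give one value per window, so only unscheduled repeats matter. If 5% to 20% of windows held one independent repeat (assumed), the mean would move by 0.05 × 0.564 = 0.03 to 0.20 × 0.564 = 0.11 SD.

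**The case against.** The windows are introduced as an example for hematology and chemistry and as something that may be defined. The rule speaks of two values, so it can be read as a tie-breaker for repeat tests and not for planned time points within a visit. This has some force: extending it to three to five readings is an inference. But the paragraph names vital signs, the worst-value sentence is firm, and nothing exempts serial readings. On the narrow reading, three or more values have no rule at all, which also needs repair.

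A worst-value summary is also defensible in a first-in-human trial for detecting infusion effects. That stands for a table of extremes. It does not justify a mean change against one baseline reading.

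The practical reach is limited. Dose-limiting toxicities (protocol 4.1.5) are event-based, infusion reactions are graded by the investigator (Appendix 10.5), and SAP 6.4.4 lists every vital sign by subject. No decision rule uses mean vital-sign change.

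A reader might infer more than the documents support:

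- That five readings, baseline included, enter the Cycle 1 Day 1 change. SAP 4.4 restricts the change to values after the first dose, so k is 4. The predose value can enter only the absolute-value summary for that window.
- That the shift is about one SD however SD is defined. That needs independent readings or the same-day SD.
- That no cohorts can be compared. Dose levels on the same schedule have the same k and remain comparable at the same visit.

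**Conclusion.** The point holds for by-visit vital-sign summaries. Applied to every reading in the window, the rule shifts the mean change with no drug effect by 0.85 to 1.16 of the same-day SD at the four schedule-visit combinations with serial readings, and by nothing elsewhere. Against the total within-subject SD, a range of about 0.4 to 0.8 is more realistic if same-day readings correlate at 0.5 to 0.75. The size rests on roughly normal readings and on an SD and a correlation that the documents do not give. The direction is not fixed for blood pressure, pulse or temperature.

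The consequences are a false time pattern and a false contrast between the two monitoring schedules. Scheduled laboratory values are unaffected unless unscheduled repeats occur. This is a worthwhile, cheap correction to descriptive safety tables; it does not threaten dose escalation or the efficacy conclusions.

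**What to change.** Amend SAP 4.4 and 6.4.4 as follows:

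- For by-visit means and changes, use one prespecified value per visit: the scheduled predose reading, or the value nearest the target day. The expected shift with no true change is then 0 at every visit.
- Summarise post-infusion vital signs by nominal time point. This table would carry the Cycle 1 Day 1 changes, since that day's predose reading serves as baseline.
- State that the Cycle 1 Day 1 predose value is excluded from the post-baseline window for absolute values too. The definition of change already excludes it from the change summary.
- Report extremes in a separate worst-post-baseline summary, with a stated direction for each parameter or with both minimum and maximum.

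The cost is SAP wording, minor programming and one added vital-sign table. The added table is needed because the by-visit means would no longer show extremes, and SAP 6.4.3 provides for shift tables only for laboratory parameters, as an option. No new data are required.
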